## LIST OF ABBREVIATIONS AND DEFINITION OF TERMS

Abbreviation	Definition
β-HCG	Beta human chorionic gonadotropin
AE	Adverse event
ALT (SGPT)	alanine aminotransferase
aPTT	Activated partial thromboplastin time
AST (SGOT)	Aspartate aminotransferase
ATC	Anatomic therapeutic classification
BSA	Body surface area
BUN	Blood urea nitrogen
CI	Confidence interval
CR	Complete response
CSR	Clinical study report
CT	Computer tomography
CTCAE	Common terminology criteria for adverse events
DCR	Disease control rate
DOR	Duration of response
ECG	Electrocardiogram
ECOG	Eastern Cooperative Oncology Group
eCRF	Electronic case report form
EORTC QLQ	European Organisation for Research and Treatment of Cancer Quality of Life Questionnaire
EOS	End of study
EOT	End of treatment
GCIG	Gynecological Cancer Intergroup
GFR	Glomerular filtration rate
GI	Gastrointestinal
HPV	Human papillomavirus
IB	Investigator's Brochure
ICH	International Conference on Harmonization
INR	International normalization ratio
IRB	Institutional review board
IWRS	interactive web-response system
Ki67	Antigen KI-67
KM	Kaplan-Meier
LDH	Lactate dehydrogenase

Abbreviation	Definition
MedDRA	Medical Dictionary for Regulatory Activities
m 	Square meter (body surface area)
mg	Milligram
mITT	Modified Intent-to-treat
mL	Milliliter
MRI	Magnetic resonance imaging
ORR	Overall response rate
OS	Overall survival
PD	Progression of disease
PDn	Pharmacodynamics
PET	Positron emission tomography
PFS	Progression-free survival
PK	Pharmacokinetics
PP	Per-protocol
PR	Partial response
PT	Prothrombin time
QoL	Quality of life
RECIST	Response Evaluation Criteria in Solid Tumors
Rel Day	Relative study day
RNA	Ribonucleic Acid
SAE	Serious adverse event
SAP	Statistical analysis plan
SD	Stable disease
SI	International System of Units
SINE	Selective inhibitor of nuclear export
SMC	Safety Monitoring Committee
SOC	System Organ Class
Std Dev	Standard deviation
SUV	Standardized uptake value
TEAE	Treatment-emergent adverse event
TUNEL	Terminal deoxynucleotidyl transferase dUTP nick end labeling
ULN	Upper limit normal
WBC	White blood cell
WHO	World Health Organization
XPO1	Exportin 1

## **1. INFORMATION FROM THE STUDY PROTOCOL**

### **1.1. Introduction and Objectives**

#### **1.1.1. Introduction**

Gynaecological malignancies include all cancer types of the woman's reproductive organs. The main types are cervical, ovarian, uterine, vaginal, and vulvar cancer. Ovarian cancer continues to be a leading cause of cancer-related deaths in women and is the leading cause of deaths attributed to gynaecological malignancies. Ovarian cancer was the eighth most common cancer in women in 2008 worldwide with roughly 235,000 new diagnoses. Approximately 140,000 women died from ovarian cancer making it the seventh leading cause of cancer death in the world (Jemal & Bray, 2011). Cervical cancer is the second most common cancer affecting women worldwide, and it remains a major health problem in developing countries because of high oncogenic human papilloma virus (HPV) infection rates, the absence of screening programs and the lack of access to affordable vaccination programs (Monk & Herzog 2007). In 2008, endometrial cancer (uterine cancer) was the 6th leading malignancy in women worldwide, approximately 288,000 new cases were diagnosed (Jemal & Bray, 2011). In 2013, endometrial cancer was the most common gynaecological malignancy in the United States and other developed countries (Siegel et al., 2013).

Ovarian, endometrial, and cervical cancers are sensitive to anti-neoplastic chemotherapy. Despite this fact, the majority of women with advanced ovarian, cervical and endometrial cancer will ultimately relapse. Altogether, in all three types of gynaecologic malignancies, the treatment of patients with advanced or relapsed disease remains difficult. Thus, new therapy options for women with these diseases are urgently needed.

Study KCP-330-005 is designed to assess the antitumor activity and safety profile of selinexor when administered orally to patients with advanced or metastatic gynecologic malignancies (including ovarian carcinoma, endometrial carcinoma, and cervical carcinoma). Selinexor is an orally available, potent Selective Inhibitor of Nuclear Export/SINE compound that specifically blocks Exportin 1 (XPO1), the major nuclear export protein in the cell, which is over expressed in many types of cancer. Further information about the preclinical and clinical characteristics of selinexor may be found in the current Selinexor Investigator's Brochure (IB).

#### **1.1.2. Study Objectives**

This statistical analysis plan (SAP) is designed to outline the methods to be used in the analysis of study data in order to address the study objectives. Populations for analysis, data handling rules, statistical methods, and formats for data presentation are provided. The statistical analyses and summary tabulations described in this SAP will provide the basis for the results sections of the clinical study report (CSR) for this trial.

This SAP will also outline any differences in the currently planned analytical objectives relative to those planned in the study protocol.

The primary and secondary objectives of the study will be addressed separately for 3 parallel cohorts of patients with ovarian carcinoma, endometrial carcinoma, and cervical carcinoma.

1.1.2.1. Primary Objective

- To determine the efficacy of selinexor in patients with advanced or metastatic gynaecological cancers by assessing disease control rate (DCR).

1.1.2.2. Secondary Objectives

- To determine the efficacy of selinexor in patients with advanced or metastatic gynaecological cancers by
  - Overall response rate (ORR)
  - Progression-free survival (PFS)
  - Overall survival (OS), including OS rates at 12 and 24 months
- To evaluate safety and tolerability of selinexor in patients with advanced or metastatic gynaecological cancers
- To evaluate Quality of Life (QoL) for patients with advanced or metastatic gynaecological cancers who are treated with selinexor

CCI

CCI

## 1.2. Study Design

### 1.2.1. Synopsis of Study Design

This trial has been designed as a multi-center, open-label, Simon two-stage, phase II study in 3 separate and parallel gynaecological cancer cohorts (i.e. Part 1), with an additional set of patients in the ovarian cohort randomized into two different treatment regimens (i.e. Part 2).

This trial has been separated into 2 parts: Part 1 and Part 2. Part 1 follows a non-randomized, single-arm, Simon two-stage optimal design in 3 separate gynaecological cancer cohorts. Part 2 follows a randomized design with 2 treatment regimens in an additional set of patients in the ovarian carcinoma cohort.

Patients are consented, screened, and enrolled in the study after histologically or cytologically confirmed and objectively documented progression of disease (PD) on prior chemotherapy documented by computer tomography (CT)/ magnetic resonance imaging (MRI). Selinexor treatment should be started within two weeks after enrollment.

Part 1: Three parallel cohorts of patients will be enrolled:

- Cohort A: Ovarian carcinoma - Patients with ovarian, fallopian tube, or peritoneal carcinoma who are platinum refractory or platinum resistant and have received at least one line of chemotherapy for relapsed disease will be enrolled. (Part 1 and Part 2)
- Cohort B: Endometrial carcinoma - Patients with endometrial carcinoma who have received at least one line of chemotherapy for relapsed or advanced (stage IVb, IIIc) disease will be enrolled. (Part 1)
- Cohort C: Cervical carcinoma - Patients with cervical carcinoma who have received at least one line of chemotherapy for relapsed or advanced (stage IV) disease will be enrolled. (Part 1)

Part 2: Based on the observed tolerability and efficacy profile in the ongoing ovarian cohort (Cohort A), two additional treatment schedules will be explored to optimize the dosing schedule in a patient population with ovarian carcinoma.

In all parts of the study, clinical and radiological examinations for disease status as well as QoL assessments will be performed at baseline, after 6 and 12 weeks of treatment, and approximately every 8 weeks thereafter.

Treatment will continue until PD or unacceptable toxicity, death, withdrawal of consent by the patient, or discontinuation of the patient due to non-compliance with protocol requirements.

Safety assessments will be performed at the baseline visit and during each cycle through the End-of-Treatment (EOT) visit.

If a patient discontinues treatment due to any reason other than PD, death, or withdrawal of informed consent, the disease evaluations shall continue until PD. This includes patients who wish to discontinue treatment, but agree to have further data captured for the purpose of the study.

After treatment discontinuation, a call will be made to the patient (or the patient's family) approximately every 3 months to inquire about the patient's survival status.

#### 1.2.1.1. Test Product, Dose, and Mode of Administration:

The dose of selinexor to be administered will be determined, by patient, on a mg/m^2 basis, based on the patient's actual calculated body surface area (BSA) at baseline. Patients with a BSA > 2.5 m^2 will receive a dose based upon a 2.5 m^2 BSA.

Each cycle is 28 days (4 weeks) long. In twice-weekly dose schedules (i.e. Part 1 and Part 2, Schedule 1), 8 doses of selinexor will be administered per cycle. In the once-weekly dose schedule (i.e. Part 2 Schedule 2), 4 doses of selinexor will be administered per cycle. Twice-

weekly doses of selinexor must be administered at least 36 hours apart; once-weekly doses of selinexor must be administered at least 5 days apart.

Dose escalations and reductions/interruptions are permitted according to safety guidelines in this protocol or in consultation with a sponsor representative (see Protocol Section 6.3).

#### Part 1:

Patients will receive oral selinexor 50 mg/m^2 twice weekly (e.g. Monday and Wednesday, Tuesday and Thursday, Wednesday and Friday or Thursday and Saturday) in each week of a 4-week cycle.

If the patient has not experienced a major toxicity after 12 weeks of treatment, a selinexor dose escalation to 60 mg/m^2 twice weekly will be allowed.

Dose reductions (minimum dose: 35 mg/m^2 once weekly) and interruptions are permitted.

#### Part 2:

There are two dosing schedules for Part 2.

- 1) Schedule 1 – Patients will receive oral selinexor 35 mg/m^2 twice weekly (e.g., Monday and Wednesday, Tuesday and Thursday, Wednesday and Friday or Thursday and Saturday) in each week of a 4-week cycle.

If there has been no major toxicity after 6 weeks, a dose escalation to 50 mg/m^2 twice weekly in each week of a 4-week cycle will be allowed.

- 2) Schedule 2 – Patients will receive oral selinexor 50 mg/m^2 once weekly in each week of a 4-week cycle (e.g., Monday of each week).

If the patient has not experienced a major toxicity after 6 weeks of treatment, a dose escalation to 60 mg/m^2 once weekly will be allowed.

Dose reductions (minimum doses - Schedules 1 and 2: 35 mg/m^2 once a week) and interruptions are permitted.

#### 1.2.2. Randomization Methodology

In Part 1, patients will not be randomized; there is only one treatment regimen.

In Part 2, patients will be randomized in a 1:1 ratio to receive Schedule 1 or Schedule 2 using centralized randomization via an interactive web-response system (IWRS). Randomization will be performed within the ovarian cohort for patients who are enrolled into Part 2 only and will not be specific to the study site. Further details on the randomization procedures can be found in a separate Randomization Plan (see Section 9.1).

#### 1.2.3. Stopping Rules

##### 1.2.3.1. Removal of Patients from Treatment

Patients will be removed from further treatment for the following reasons:

- Disease progression (PD)
- Adverse event (unacceptable toxicity)
- Non-compliance
- Need of treatment with medications not allowed by the study protocol

- Patient no longer consents to participate in the study
- Intercurrent illness that interferes with study assessments
- Incidence or severity of AEs in this study indicates a potential health hazard to the patient
- Investigator discretion
- Pregnancy
- Termination of the study by the Sponsor

When a patient discontinues study treatment, the EoT visit should be performed, if possible. The eCRF section entitled “End of Treatment” must be completed in all cases. If the reason for removal of a patient from the study is an AE or abnormal laboratory test result, the principal specific event or test will be recorded on the eCRF.

If a patient is discontinued from study treatment, the patient should still be followed for PD and survival. If a patient withdraws consent for further participation in the study, follow-up assessments will be discontinued.

#### 1.2.3.2. Study Discontinuation

The study may be discontinued at the sole discretion of the Sponsor for any reason, including medical or ethical reasons affecting the continued performance of the study, or difficulties in the recruitment of patients. Medical reasons may include, but are not limited to, such features as deemed by the Safety Monitoring Committee (SMC) to constitute an unacceptable risk to the patients in the study, such as lack of efficacy or Serious Adverse Events (SAEs), such as Grade 4 anorexia and fatigue unresponsive to medical treatment.

The sponsor (Karyopharm), in conjunction with appropriate regulatory authorities, will determine if the trial should be modified or terminated. If this occurs, the sponsor will notify Institutional review board (IRB) and Investigators.

#### 1.2.4. Study Procedures

The schedule of assessments, as outlined in the study protocol, is presented in Table 1-1.

**Table 1-1 Schedule of Assessments**

Assessment	Baseline (Within 14 days prior to Cycle 1 Day 1)	Day 1 of each Cycle (up to -3 days)	Day 15 of each Cycle (± 3 days)	After 6 weeks of treatment (±7 days)	After 12 weeks of treatment and every 8 weeks (± 7 days) thereafter until PD	EOT (30 days ± 7 days after last dose of selinexor)	Survival status (every 3 months)
Informed consent 	X						
Inclusion and exclusion criteria	X						
Demographics	X						
Medical history 	X						
Pregnancy test (if applicable) 	X						
Physical examination and ECOG 	X	X				X	
Neurological examination 	X						
Body height and weight 	X	X	X			X	
BSA	X	X					
Vital signs 	X	X				X	
Ophthalmic exam 	X						
12-lead ECG 	X					X	
Pulse oximetry 	X					X	
Hematology 	X	X	X			X	
GFR Calculation  (or measurement)	X						
Clinical Chemistry 	X	X	X			X	
Urinalysis 	X					X	
Coagulation test 	X						
CA-125 (for Cohort A only)	X	X					
Gynecological examination	X			X (optional)	X	X	
CT/MRI chest and abdomen 	X			X	X		
PET-CT 	X			X	X		

Assessment	Baseline (Within 14 days prior to Cycle 1 Day 1)	Day 1 of each Cycle (up to -3 days)	Day 15 of each Cycle (± 3 days)	After 6 weeks of treatment (±7 days)	After 12 weeks of treatment and every 8 weeks (± 7 days) thereafter until PD	EOT (30 days ± 7 days after last dose of selinexor)	Survival status (every 3 months)
EORTC QLQ-C30 	X			X	X	X	
Adverse Events (AE)	X (SAEs beginning at informed consent form signing; AEs beginning at first dose)						
Concomitant medication	X	X	X	X	X	X	
Selinexor dosing 		X	X				
Required supportive care 	X	X	X				
Telephone contact 							X

CCI CCI CCI

1. Informed consent required prior to the first study-specific measures.
2. Medical history includes baseline symptoms as well as a detailed history of prior cancer therapies including start and stop dates, disease progression during or after therapy, as well as discontinuations due to intolerance or any other serious illness.
3. Pregnancy test applicable for women of childbearing potential. Serum beta human chorionic gonadotropin (β-HCG) test within 7 days before the first dose of study drug. To be repeated by urine test, if date of first result exceeds the 7-day window. Urine pregnancy testing is to be performed as clinically indicated during the study. Any positive urine pregnancy test must be confirmed with a serum β-HCG test.
4. Full physical examination and ECOG at baseline and End of Treatment (EOT) visit. All other physical examinations during the study should be symptom directed.
5. A standard neurological examination to assess motor, sensory, and balance functions to be performed.
6. Body height will be measured at screening only.
7. Vital signs will include blood pressure, pulse, and temperature.
8. Full ophthalmic exam: by an optometrist or ophthalmologist is required at screening and if clinically indicated during the study (e.g. monitoring of pre-existing cataracts, visual disturbances). *Please note:* Patients enrolled under a prior version of the protocol who had detectable cataracts graded according to the LOCS III will continue to have their cataracts graded according to LOCS III and will not switch to the American Optometric Association (AOA) scale. For new patients or patients for whom no cataracts have been detectable to date, if cataracts are detected they will be graded according to the AOA scale.

9. 12-Lead ECG performed at screening, End of Treatment final visit, and if clinically indicated during the study.
  10. Pulse oximetry is performed for patients at rest while breathing room air.
  11. Hematology: includes hemoglobin, white blood cell (WBC) count, neutrophils, and platelets. Blood draws can be done 3 days prior to visit.
  12. Calculated glomerular filtration rate (GFR) according to the formula of *Cockcroft and Gault*.
  13. Clinical chemistry: includes sodium, potassium, chloride, bicarbonate, blood urea nitrogen (BUN), creatinine, glucose, calcium, phosphate, magnesium, alanine aminotransferase (ALT), aspartate aminotransferase (AST), alkaline phosphatase, total bilirubin, lactate dehydrogenase (LDH), total protein, and albumin. Blood draws can be completed 3 days prior to the visit; testing may be repeated on the day of the visit if clinically indicated.
  14. Urinalysis will include urine bilirubin, glucose, hemoglobin, ketones, pH, and protein. Performed at screening, at the End of Treatment visit, and if clinically indicated.
  15. Coagulation-test includes prothrombin time (PT), international normalization ratio (INR), and activated partial thromboplastin time (aPTT). This will be performed at baseline and if clinically indicated. Blood draw can be done up to 3 days prior to visit.
  16. CT/MRI of abdomen must include pelvis. PET-CT is allowed, but ultrasound of the abdomen and x-ray of thorax is not allowed. CT/MRI or PET/CT scans to be performed within four weeks prior to registration. CT scan is required again if patient has relapse and if clinically justified during trial period. On-study tumor assessment should be performed after 6 weeks ( $\pm$  7 days) and 12 weeks ( $\pm$  7 days) of treatment. Thereafter, tumor assessments will be performed every 8 weeks ( $\pm$  7 days) thereafter, independent of cycle delays, until disease progression or death.
  17. Patients to complete the EORTC QLQ-C30 at baseline, with tumor assessment during treatment (i.e. at Week 6, Week 12 and every 8 weeks thereafter), and at the End of Treatment visit.
  18. Selinexor dosing for Part 1, and Part 2, Schedule 1: Twice weekly (e.g., Monday and Wednesday, Tuesday and Thursday, Wednesday and Friday or Thursday and Saturday) in each week of a 4-week cycle; Part 2, Schedule 2: Once weekly dosing in each week of a 4-week cycle (e.g., Monday of each week). For dosing details, including delayed doses and changes to the visit schedule, see Protocol Section 6.2.2 and Section 6.3).
  19. All patients will receive required supportive care to prevent nausea, as described in Protocol Section 6.5.1.
- CCI
- CCI
23. After treatment discontinuation, a call will be made to the patient (or the patient's family) approximately every 3 months to inquire about the patient's survival status.

### 1.2.5. Efficacy, CCI [REDACTED] and Safety Parameters

#### 1.2.5.1. Efficacy Parameters

The primary efficacy endpoint is DCR, defined as complete response (CR) or partial response (PR) or stable disease (SD) for at least 12 weeks, assessed according to Response Evaluation Criteria in Solid Tumors (RECIST) v1.1. Supportive data will be provided by Duration of SD, calculated from the date of start of study therapy until the date of PD, or last disease assessment should PD not have occurred.

The secondary efficacy endpoints for all cohorts include:

1. Response to therapy per RECIST v1.1, as determined by ORR, defined as either CR or PR per RECIST v1.1, including duration of response (DOR)
2. PFS, calculated from the date of start of study therapy to the date of PD per RECIST v1.1 or date of death if PD does not occur
3. OS, calculated from the date of start of study therapy to the date of death due to any cause, including OS rates at 12 and 24 months
4. QoL, evaluated by the EORTC QLQ-C30

Additional secondary endpoints for the ovarian cancer cohort only include the following:

1. Response to therapy, as determined by DCR, Duration of SD, ORR, and DOR per Gynecological Cancer Intergroup (GCIG) response criteria (RECIST v1.1 and CA-125) (Rustin et al, 2011)
2. PFS, as described above with progression defined per GCIG response criteria (RECIST v1.1 and CA-125)

Data from Part 1 and Part 2 of the study will be analyzed separately for all primary and secondary efficacy endpoints.

CCI [REDACTED]

#### 1.2.5.3. Safety Parameters

Safety evaluations performed during the study include physical, neurological, and ophthalmic examinations; measurement of vital signs; 12-lead electrocardiogram (ECG); clinical laboratory evaluations including hematology, clinical chemistry, and urinalysis; and monitoring of AEs and concomitant medications.

#### 1.2.5.4. Safety Monitoring Committee

A Safety Monitoring Committee (SMC) will provide additional oversight on the safety of the investigational product, selinexor (KPT-330), as used in this study. The SMC is responsible for reviewing accumulated safety data from the study.

The SMC will have access to all data necessary to formulate their opinion on the safety of the study. This includes efficacy data at the scheduled meetings as this is relevant to assessing the acceptability of the AE profile observed.

## **2. PATIENT POPULATIONS**

### **2.1. Population Definitions**

The following patient populations will be evaluated and used for presentation and analysis of the data:

- **Modified Intent-to-Treat (mITT) Population:** All patients who receive at least one dose of study medication, have measurable disease per RECIST at baseline, and have at least one post-baseline efficacy follow-up information. If the patient has measurable disease per RECIST at baseline, but discontinued treatment prior to the first assessment due to death, toxicity, or PD, they will still be included even if there is no post-baseline efficacy follow-up information. This population will be used for primary analyses of efficacy.
- **Per-Protocol (PP) Population:** All patients in the mITT population who are compliant with study assessments and who have no protocol violations that would compromise the assessment of efficacy. This population will be used for supportive inferences concerning efficacy. If there are major differences between the results in this population and those obtained in the mITT population, this will be taken into consideration in the decision to continue to later phase studies, or in the design of further studies.
- **GCIG Evaluable Population:** All patients in the ovarian cancer cohort (Cohort A) who receive at least one dose of study medication, have measurable disease per RECIST at baseline or a baseline CA-125 assessment, and have at least one post-baseline efficacy follow-up information (i.e. either a post-baseline scan or CA-125 assessment). If a patient discontinued treatment prior to the first assessment due to death, toxicity, or PD, they will still be included even if there is no post-baseline efficacy follow-up information. This population will be used for additional efficacy analyses specific to patients with ovarian cancer.
- **mITT Extended Population:** All patients who receive at least one dose of study medication and have at least one post-baseline efficacy follow-up information. If the patient discontinued treatment prior to the first assessment due to death, toxicity, or PD, they will still be included even if there is no post-baseline efficacy follow-up information. This population will be used for supportive efficacy analyses of select time-to-event endpoints (PFS and OS).
- **Safety Population:** All patients who have received any amount of study medication. This population will be used as the primary population for analysis of all safety endpoints.

Analysis of efficacy parameters in Part 2 will be based on the randomized treatment assignment for Part 2. Analysis of safety parameters will be based on treatment received, even if different from that randomized in Part 2.

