2. *Response to therapy per GCIG response criteria (RECIST 1.1 and CA-125)*: response for patients in the ovarian cohort will also be assessed for DCR and ORR, as described above, using the GCIG response criteria. Only patients with sufficient data to be assessed based on this criteria (i.e., has a baseline CA-125 assessment) will be included. Number and frequency of patients in the ovarian cancer cohort who can be assessed using the GCIG response criteria will be presented.
3. *Median Progression-free Survival*: PFS for patients in each cohort will be calculated from the date of start of study therapy to the date of progression based on RECIST 1.1, or date of death should progression not have occurred. Patients who drop out prior to study end or do not have documented PD will be censored at the day of last documented disease assessment. The analysis of PFS for patients in each cohort will be based on the Kaplan-Meier method for estimation of summary statistics, and include the 25th, 50th (median), and 75th percentiles and associated 95% CIs. PFS will also be presented with progression defined per GCIG response criteria (RECIST 1.1 and CA-125) for patients in the ovarian cohort with sufficient data to be assessed based on this criteria (i.e., has a baseline CA-125 assessment).
4. *Overall Survival*: OS for patients in each cohort will be calculated from the date of start of study therapy to the date of death due to any cause. OS rate at 12 and 24 months will also be calculated. Patients who drop out prior to study end will be censored at the day they were last known to be alive. The analysis of OS for patients in each cohort will be based on the Kaplan-Meier method for estimation of

summary statistics, and include the 25th, 50th (median), and 75th percentiles and associated 95% CIs.

5. *Quality of Life (QoL)*: will be evaluated for patients in each cohort, and for all study patients combined by EORTC QLQ-C30 after 6 and 12 weeks of treatment and approximately every 8 weeks thereafter.

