Appendix 12: Evaluation of Response According to CA-125

(Modified from *Rustin, Vergote, Eisenhauer et al*)

A CA-125 response is defined as at least a 50% reduction in CA-125 levels from a pretreatment sample. The response must be confirmed and maintained for at least 28 days. Patients can be evaluated according to CA-125 only if they have a pretreatment sample that is at least twice the upper limit of the reference range and within 2 weeks before starting the treatment.

To calculate CA-125 responses accurately, the following rules apply:

- Intervening samples and the 28-day confirmatory sample must be less than or equal to (within an assay variability of 10%) the previous sample.
- Variations within the reference range of CA-125 levels will not interfere with the response definition.
- For each patient, the same assay method must be used, and the assay must be tested in a quality control scheme.
- Patients are not evaluable by CA-125 if they have received mouse antibodies (unless the assay used has been shown not to be influenced by human anti-mouse antibody) or if there has been medical and/or surgical interference with their peritoneum or pleura during the previous 28 days (e.g., paracentesis). If assessing therapy that includes 2 treatment modalities for relapse (e.g., surgery and chemotherapy), any CA-125 response results from both treatment modalities. CA-125 cannot distinguish between the effects of the 2 treatments

The date when the CA-125 level is first reduced by 50% is the date of the CA-125 response. To calculate response, an intent-to-treat analysis should be used that includes all patients with an initial CA-125 level of at least twice the upper limit of the reference range as eligible and evaluable. In addition, as a separate analysis, those patients who have a CA-125 response and whose CA-125 level falls to within the reference range can be classified as CA-125 complete responders.

In [Table 9 \(Appendix 13\)](#) and [Table 10 \(Appendix 14\)](#) where CA-125 is stated as normalized or normal, means within the reference range. Patients who have a fall of CA-125 to within the reference range but whose initial CA-125 was less than twice the upper limit of the reference range have not had a CA-125 response and cannot therefore be classified as a CA-125 complete responder.

Appendix 13: Evaluation of Best Overall Response in Patients Without Initial Measurable Disease and Who Are Evaluable by CA-125

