### **3.8. Subpopulations**

Part 1 of the study will enroll three cohorts of ovarian (Cohort A), endometrial (Cohort B), and cervical (Cohort C) cancers which will be evaluated independently. Part 2 of the study will enroll additional ovarian patients to evaluate efficacy and safety of once-weekly versus twice-weekly dosing.

Subtypes of each tumor (e.g., adenocarcinoma versus squamous carcinoma) will be evaluated both together and separately as exploratory analyses.

The subpopulation of ovarian cancer (Cohort A) patients who have a baseline CA-125 assessment will be evaluated per the GCIG response criteria in secondary analyses. Within the secondary analyses, a further subpopulation of patients with an initial CA-125 level of at least twice the upper limit of the reference range will be assessed.

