## 5. CHANGES TO PLANNED ANALYSES

CCI

In Protocol Section 8.4.1, it is noted that no imputation of missing efficacy data is planned. In Section 3.10 of this document, it is noted that partial time-to-event dates with only month and year available will be imputed by setting the day to the first day of the month.

Protocol Section 8.3 describes 3 populations (mITT, PP, and Safety population) to be used for study analyses. In Section 2.1 of this document, two additional populations are included, the GCIG Evaluable population and the mITT Extended population. In addition, the mITT population definition is updated to include the criterion that patients have measurable disease per RECIST v1.1 at baseline.

[figure not shown]

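### SAP 2.1 admits ovarian patients without a baseline CA-125 to the GCIG analyses, although Protocol 8.4.3 and SAP 3.8 require one and the readable text of SAP 5 does not declare the change

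*SAP*

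**What the plan says.** SAP 2.1 (Population Definitions) admits to the GCIG Evaluable Population Cohort A patients who took at least one dose and "have measurable disease per RECIST at baseline or a baseline CA-125 assessment". They also need post-baseline information, "i.e. either a post-baseline scan or CA-125 assessment". Early discontinuation for death, toxicity or PD waives that last condition.

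SAP 3.8 (Subpopulations) describes the set differently. The Cohort A "patients who have a baseline CA-125 assessment will be evaluated per the GCIG response criteria in secondary analyses", and within these "a further subpopulation of patients with an initial CA-125 level of at least twice the upper limit of the reference range will be assessed".

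Protocol 8.4.3, secondary analysis 2 (GCIG DCR and ORR), is explicit: "Only patients with sufficient data to be assessed based on this criteria (i.e., has a baseline CA-125 assessment) will be included". Secondary analysis 3 applies the same condition to GCIG PFS, which is "for patients in the ovarian cohort with sufficient data to be assessed based on this criteria", again explained as having a baseline CA-125.

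SAP 4.3.2 runs DCR, duration of SD, ORR and DOR (item 2) and PFS (item 3b) on a GCIG Efficacy Population, a name that SAP 2.1 does not define. Item 2 adds a subset analysis in patients whose initial CA-125 is at least twice the upper limit of normal (ULN).

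SAP 5 (Changes to Planned Analyses) states that "two additional populations are included, the GCIG Evaluable population and the mITT Extended population". Its readable text does not mention the baseline CA-125 condition.

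**The concern.** The same endpoints have two entry rules. The either/or in SAP 2.1 lets in a patient with measurable disease and no baseline CA-125, whom Protocol 8.4.3 and SAP 3.8 leave out. The SAP gives no tie-breaker, because the analysis section uses a population name that is not defined.

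The denominators of the GCIG endpoints, in Part 1 and in each Part 2 schedule, therefore depend on which sentence the programmer follows. The wider rule also brings in patients for whom the SAP's own response table has no complete classification, so a further unwritten decision is needed. Both choices could be made after the data are known.

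**Working it through.** The plan states no figure to reproduce, so the check compares the texts and then gives an illustration.

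**1. Entry rules side by side**

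| Source | Who enters the GCIG analyses |
|---|---|
| SAP 2.1 | Measurable disease **or** baseline CA-125 |
| SAP 3.8 | Baseline CA-125 |
| Protocol 8.4.3, item 2 (DCR, ORR) | Baseline CA-125 only |
| Protocol 8.4.3, item 3 (PFS) | Baseline CA-125 |
| SAP 4.3.2, items 2 and 3b | GCIG Efficacy Population (not defined) |
| SAP 5, readable text | Population added; dropped condition not mentioned |

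The rules differ for exactly one group: measurable disease, no baseline CA-125.

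**2. Can the response rules classify that group?**
- SAP Table 4-1 defines CA-125 CR, PR, Normalized and PD by reference to a pretreatment or baseline value. Without one, none of the four can be derived.
- In SAP Table 4-3, the rows leading to overall CR, PR or SD all require a CA-125 entry (Normal, PR, Not PD, or Not PR/Not PD). No row is provided for missing CA-125.
- The rows that accept any CA-125 result all lead to PD.
- Protocol Appendix 14, the source of Table 4-3, covers patients with measurable disease who are also evaluable by CA-125.

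So, as written, such a patient is PD or has no GCIG response. For PFS, her event can come only from RECIST progression or death.

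**3. How many patients?** The documents give no count.
- Pointing to some: the study started in January 2014, and the amendment history records CA-125 collection for ovarian patients as added in Version 2.0 (September 2014) and a baseline CA-125 assessment as added in Version 3.1 (January 2016).
- Pointing to few: the current schedule has CA-125 at baseline and on Day 1 of each cycle, and SAP 3.4 takes the most recent pre-dose measurement as baseline. A pre-dose Cycle 1 Day 1 sample would count.

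**4. Illustration of size.** Let N be the group size: about 21 in Part 1 and 16 per Part 2 schedule (Protocol 3.2). Let k be the number without CA-125 and p the rate among the classifiable patients. Both k and p are assumed.

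If the k patients count as failures, the reported rate is p × (N − k)/N. For p = 50%:

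| k | N = 21 | N = 16 |
|---|---|---|
| 0 | 50.0% | 50.0% |
| 1 | 47.6% | 46.9% |
| 2 | 45.2% | 43.8% |
| 3 | 42.9% | 40.6% |
| 4 | 40.5% | 37.5% |

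For p = 25% and k = 4 the rate is 20.2% (N = 21) or 18.8% (N = 16).

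If the k patients are instead given their RECIST result, with rate q, the reported rate is [p(N − k) + qk]/N. It differs from p by (q − p)k/N, whose sign depends on q and p. If they are dropped as unclassifiable, the estimate is p on N − k patients, which is the Protocol 8.4.3 analysis.

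**The case against.** **SAP 5 does declare the population.** It names the GCIG Evaluable population as an addition and points to SAP 2.1, where the rule is written out, and it opens with a redacted block. This stands in part: the population is disclosed, and an explanation could lie under the redaction. But the readable text spells out the criterion added to mITT and says nothing of the condition removed here. SAP 3.8 would still contradict SAP 2.1.

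**Table 4-1 has a residual category.** Non-PR/Non-PD applies when none of the other definitions is met, and a programmer could place missing CA-125 there. The SAP does not say so. It would open the SD row, but the note to Table 4-3 that explains Not PD lists only Normalized, CR and PR, so a RECIST partial response would still have no row. This confirms that the outcome rests on an unwritten choice.

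**A tempting stronger reading is that at least twice ULN is a third entry rule**, making patients below it unassessable for every GCIG endpoint. Protocol Appendix 12 does say "Patients can be evaluated according to CA-125 only if they have a pretreatment sample that is at least twice the upper limit". But that appendix governs CA-125 response. Table 4-1 defines CA-125 progression for a normal baseline, and Table 4-2 gives SD to patients who normalize without a CA-125 response. Protocol 8.4.3 treats a baseline CA-125 as sufficient, and SAP 4.3.2 already plans the twice-ULN subset. Making that subset the main set for ORR and DOR would itself depart from Protocol 8.4.3.

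**A related reading is that patients with no measurable disease and CA-125 below twice ULN fill the ORR denominator as patients who cannot respond.** Inclusion criterion 17 requires ovarian disease to be measurable or assessable by the GCIG CA-125 criterion. If Appendix 12 defines assessable, such patients are ineligible under the current text. The criterion was revised in Version 3.0, so earlier enrolment is uncertain.

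**Conclusion.** The contradiction stands in a narrow form. SAP 2.1 is wider than Protocol 8.4.3 and SAP 3.8, the readable SAP does not declare the difference, and the added patients have no complete classification in Table 4-3.

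The size is unknown and may be zero or small. In the illustration, each unclassified patient counted as a failure costs 2.4 percentage points at N = 21 (0.50/21) or 3.1 at N = 16 (0.50/16). This assumes a 50% rate among classifiable patients, which the documents do not give for any GCIG endpoint.

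A reader might infer that GCIG ORR is biased downward, or that GCIG PFS is pulled toward RECIST PFS by a material amount. The documents support neither: they give no missing count, no rates for the two groups and no rule for missing CA-125, so the direction is undetermined. Only secondary ovarian endpoints are involved. The primary DCR uses RECIST on the mITT population and does not change.

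**What to change.** - In SAP 2.1, replace the either/or condition with a required baseline CA-125, matching Protocol 8.4.3 and SAP 3.8.
- Use one name for this population in SAP 2.1 and 4.3.2, in place of GCIG Evaluable and GCIG Efficacy.
- If the wider set is kept, present it as supportive, declare it in SAP 5 as a departure from Protocol 8.4.3, and state how a missing CA-125 is classified in Table 4-3.
- Keep the twice-ULN set as the subset analysis already planned in SAP 4.3.2, and state that it concerns CA-125 response and does not restrict GCIG PFS.

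The cost is SAP wording; no new data are needed. The downside is a slightly smaller denominator for secondary ovarian endpoints.
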